16.1.4 Allocation of TEAEs to Study Periods

TEAEs will be assigned to periods according the following:

- Adverse events in the double-blind period (DBP) all TEAEs with date of onset or worsening of intensity/seriousness after first dose of IMP in the DBP and until first dose of IMP in the OLE period (planned for Visit 1E – for patients entering the OLE) or the Safety Follow up visit for the DBP (SFU Visit 25 – for patients NOT entering the OLE) (assigned APHASE = DOUBLE BLIND).
- Adverse events in the Open-Label Extension period TEAEs with date of onset or worsening of intensity/seriousness after first dose of IMP in the OLE period (Visit 1E) and until the final Safety Follow up visit for the OLE (Visit 64E) (assigned APHASE = OLE).

The above imply that an adverse event, with multiple levels of intensity/seriousness, may be reported for more than one phase but only if it worsens. For instance, an adverse event ongoing at the end of the End-of-Treatment (EoT) visit which worsens after the first dosing in the OLEP, will be reported both for the double-blind period (DBP) and for the open-label period, but an adverse event ongoing at the EoT visit, which reduces in intensity/severity will only be reported in the DBP.

16.1.5 Presentation of Adverse Events

All adverse events will be listed for the APRS.

An overview of the PYE and number and percentage of patients with TEAEs, serious adverse events (SAEs), or adverse events leading to withdrawal, and of patients who died will be provided based on the APTS for the open-label and safety follow-up period.

For TEAEs, SAEs, and adverse events leading to withdrawal/death, the total number of events will be included.

16.1.6 Presentation of Treatment-emergent Adverse Events

For TEAE's, the following summaries will be provided by study period (DBP, OLEP and the safety follow-up periods, if appropriate) for the APTS:

- TEAEs by SOC and preferred term
- TEAEs by preferred term
- TEAEs with an incidence \geq 5% by preferred term
- TEAEs by causality (possible, probable, not related), SOC and preferred term
- TEAEs by intensity (*mild/moderate/severe*), SOC, and preferred term

The summaries will be provided for the APTS for the study periods.

For TEAEs occurring on the day of dosing after infusion start, TEAEs with missing start times will also be included.

16.1.7 Presentation of Deaths

All the adverse events in patients who died will be listed for the APRS.

16.1.8 Presentation of Serious Adverse Events

All the SAEs will be listed for APRS by study period.

Treatment-emergent SAEs for the APTS will be summarized by:

- SOC and preferred term
- preferred term

16.1.9 Presentation of Adverse Events Leading to Withdrawal

All the adverse events leading to withdrawal will be listed for the APRS.

TEAEs leading to withdrawal will be summarized by:

- SOC and preferred term
- preferred term

16.1.10 Presentation of Adverse Events Leading to Study Drug Infusion Interruption or Infusion Rate Reduction

All AEs leading to study drug infusion interruption or infusion rate reduction will be listed for the APRS.

TEAEs leading to study drug infusion interruption or infusion rate reduction will be summarized based on APTS by:

- SOC and preferred term
- preferred term

16.1.11 Presentation of Adverse Events requiring additional data collection

Treatment-emergent adverse events related to Type I, II and III Hypersensitivity reactions have been defined as study-specific AE's requiring additional data collection. Events considered Hypersensitivity reactions by the Investigator will be collected during the study using a dedicated Hypersensitivity Form.

Summaries will be provided for each period for the APTS for Hypersensitivity Reactions (as reported by the investigator) and for each of the following sponsor defined categories (see Appendix VI).

- TEAEs with a PT within the SMQ of Hypersensitivity (narrow scope)
- TEAEs with a PT 'Cytokine release syndrome'
- TEAEs with a PT within the SMQ Vasculitis (narrow scope) or any of the 15 defined single PTs

Hypersensitivity reactions will be listed by category by the APRS.

16.2 General Methodology for Other safety Data

Unless otherwise specified, tables, graphs, and listings will be based on the APTS.

All tables and graphs will be presented by treatment group.

The denominators for the summaries of a given variable will be based on the number of patients with non-missing values at a given visit or during the assessment period.

Descriptive statistics for the safety variables, both absolute values and changes from baseline, will be presented by visit, separately for each period.

The number and percentage of patients with at least one PCS value at any post-baseline assessment time point will be summarized by variable, separately for each period. All available assessments in each period will be included in the evaluation of PCS values.

For patients with post-baseline PCS values, listings will be provided including all the values for those patients for the variable, with flagging of PCS values and out-of-reference-range values.

For vital signs being measures multiple time during a visit values will be presented graphically within visit over time, where the position will be indicated.

All the adverse events in patients with post-baseline PCS values will be listed by treatment group and patient screening number; the listing will include the PCS value, the assessment date, the change from baseline in PCS value, the preferred term for the adverse event, and start date and stop date of the adverse event. The PCS values and adverse events will be listed in chronological order according to assessment date and the start date of the adverse event

16.3 Clinical Safety Laboratory Test Data

16.3.1 Data Presentation

The PCS criteria used for the clinical safety laboratory tests can be found in Appendix V.

The clinical safety laboratory test values will be presented both in conventional and Système International (SI) units.

16.4 Vital Signs and Weight

The PCS criteria used for vital signs and weight are the Lundbeck standard PCS criteria described in SOP_09978: *GPV* – *PCS and standard reference values for laboratory investigations, vital signs and ECGs in clinical studies*, version 6, and are also included in Table 4.

16.5 ECG

The PCS criteria used for the ECG parameters are the Lundbeck standard PCS criteria described in SOP_09978: *GPV – PCS and standard reference values for laboratory investigations, vital signs and ECGs in clinical studies*, version 6, and are also included in Table 5.

In addition to the tables and listings specified in section 16.2, absolute values and changes from Baseline in QTcF will also be summarized categorically by visit and treatment. The categories that will be used are as follows for the absolute QTcF values:

- QTcF interval < 450 msec
- QTcF interval 450 480 msec
- QTcF interval > 480 500 msec
- QTcF interval > 500 msec

The categories that will be used for the change from baseline QTcF values are:

- QTcF interval increase from baseline > 30 msec
- QTcF interval increase from baseline > 60 msec

Furthermore, the number and percentage of patients being classified as having either a normal, abnormal but not clinically significant, abnormal and clinically significant, or not interpretable ECG result based on the overall interpretation of the ECG from the investigator will be summarized by visit and treatment group.

16.6 Columbia-Suicide Severity Rating Scale (C-SSRS) Scores

The C-SSRS was administered:

- for Screening at Visit 1: The C-SSRS assessment that collects a lifetime and 6 months recall (using the *Baseline/Screening Version*)
- for Baseline at Visit 3: The C-SSRS assessment that collects a lifetime and 6 months recall (using the *Baseline/Screening Version*)
- For subsequent visits: The C-SSRS assessment that collects information since the previous visit (using the *Since Last Visit Version*)

The numbers and percentages of patients with lifetime, 6 months pre-baseline or post-baseline suicide-related events based on the C-SSRS will be summarized by treatment group. For each summary, the most severe item with an answer "Yes" for each patient according to the ordering given in Panel 3 is displayed. For the post-baseline assessments, the summaries will be by treatment group and the most severe item with an answer "Yes" for the whole period for each patient related to suicidal ideation and/or behaviour will be summarized.

The number and percentage of patients with *no suicidal ideation or behaviour* will be included in the summaries.
C-SSRS S	Score	Related to:
1	Wish to be dead	Suicidal ideation
2	Non-specific active suicidal thoughts	
3	Active suicidal ideation with any methods (not plan) without intent to act	
4	Active suicidal ideation with some intent to act, without specific plan	
5	Active suicidal ideation with specific plan and intent	
6	Preparatory acts or behaviour	Suicidal behaviour
7	Aborted attempt	
8	Interrupted attempt	
9	Non-fatal suicide attempt	
10	Completed suicide (only applicable for the post-baseline assessments)	

Panel 3 C-SSRS Scores

The C-SSRS scores will be summarized based on the APTS.

Missing C-SSRS scores will not be imputed.

Positive responses to non-suicidal self-injurious behaviour will be summarized separately.

For patients with any post-baseline suicidal ideation or behaviour (C-SSRS scores of 1 to 10), listings will be provided based on APRS including all C-SSRS scores for those patients

16.7 MRI Safety Findings

MRI safety findings will be listed.

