#### **Safety Endpoints**

Double-blind Period

- Treatment-emergent adverse events
- Absolute values and changes from baseline in clinical safety laboratory test values, vital signs, weight, and electrocardiogram (ECG) parameter values
- Development of specific anti-drug antibodies (ADAs)
- Findings on MRI during the DBP, as specified in the *Imaging* Charter
- Columbia-Suicide Severity Rating Scale (C-SSRS) score
- To evaluate safety and tolerability of Lu AF82422 in patients with MSA in the Open-label Extension Period

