#### Analysis of OLE efficacy data:

- Analysis of exploratory efficacy data collected in the OLE will be based on the OLES where the original placebo patients will be handled as a separate group.
- All continuous endpoints following treatment extension will primarily be analyzed descriptively. In addition, an exploratory MMRM will be applied to the changes from the DBP baseline visit. No formal testing will be applied. Further details on the model will be outlined in the Statistical Analysis Plan (SAP).

[figure not shown]
A study-specific SAP will be developed for this study to describe further details on the proposed analyses. In addition, there will be a separate *Psychometric SAP* which will include the description of the methods and analytical principles to preliminarily explore in this study the psychometric properties and the meaningful within-patient change of the UMSARS TS, mUMSARS and aUMSARS.

- Patient disposition and demographics will be summarized using descriptive statistics.
- Reason for withdrawal will be investigated and compared between Lu AF82422 and placebo.
- The use of concomitant medication will be analyzed descriptively.
- Analysis of safety endpoints:
  - The safety analyses will be based on the APTS and the OLES.

Treatment-emergent adverse events, clinical safety laboratory tests, vital signs, weight/body mass index (BMI), ECG parameters, C-SSRS, MRI findings, and presence of ADAs will be summarized using descriptive statistics.

[figure not shown]

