#### 5.1 Ethical Rationale

The ethical rationales for this study are the following:

- There is an unmet medical need for a treatment that can delay the progression in MSA, addressed by this study
- The justification of the study design is provided in section 4.2
- Establishing an iDMC because:
  - -MSA is a new indication, and in the FIH SAD study only a few patients with another type of α-synucleinopathy (Parkinson's disease) were exposed to Lu AF82422. No MSA patients have previously been exposed to Lu AF82422.
  - -Use of a mAb, a new therapeutic, where other entities of the class had effects on the CNS.
  - -Limited safety data overall are available on Lu AF82422 (low number of subjects exposed to a single dose of Lu AF82422).

The patient will be fully informed about the study including the risks and benefit of his/her participation in the study.

The patient may withdraw from the study at any time, for any reason, specified or unspecified, and without penalty or loss of benefits to which the patient is otherwise entitled.

Information on race will be collected to support future filing claims in the US according to Food and Drug Administration (FDA) guidance document and ICH E17 guideline on general principles for planning and design of multi-regional clinical trials.

In accordance with *Good Clinical Practice*, qualified medical personnel at Lundbeck or designated clinical research organization (CRO) will be readily available to advise on study-related medical questions. Medical monitoring and safety review will be performed throughout the study. In addition, safety data will be reviewed regularly by the Lundbeck Lu AF82422 Safety Committee to ensure that prompt action is taken, if needed.

In accordance with *Good Clinical Practice*, the investigator will be responsible for all study-related medical decisions.

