#### 17.10.2 Analysis of Other Safety Endpoints

The clinical safety laboratory test values, vital signs, ECG parameter values, ADA, safety MRI findings and C-SSCS will be summarized by period and treatment group. Potentially clinically significant (PCS) values will be flagged and summarized.

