4.4 Safety Endpoints

4.4.1 Double-Blind Period

- Treatment emergent adverse events
- Absolute values and changes from baseline in clinical safety laboratory test values, vital signs, weight, and ECG parameter values
- Development of specific anti-drug antibodies (ADA)
- Findings on MRI, as specified in the *Imaging Charter*
- Columbia-Suicide Severity Rating Scale (C-SSRS) score

4.4.2 **Open-label Extension Period**

- Treatment-emergent adverse events
- Absolute values and changes from baseline in clinical safety laboratory test values, vital signs, and weight parameter values
- Development of specific anti-drug antibodies (ADAs)
- Columbia-Suicide Severity Rating Scale (C-SSRS) score

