20 Interim Analyses

No interim analyses will be conducted for this study.

21 Sample Size Considerations

The 18331A sample size has been selected to ensure an appropriate power to detect a 40% slowing in MSA progression in the Lu AF82422 CO dose group compared to the placebo group on a 5% significance level evaluated 1-sided. Applying a repeated measures model with proportional treatment effect, yields an approximate 75% power when having N=60 patients allocated 2:1 in favour of Lu AF82422 treatment (i.e., 40 on Lu AF82422 *versus* 20 on

Study 18331A - Statistical Analysis Plan

placebo) when using the NLMIXED procedure for simulating in SAS[®]. To account for differences in treatment duration due to the study design, approximately 50% of the patients are expected to contribute with 60 weeks data and 25% of the patients with full 72 weeks data. On top, an overall 20% drop-out rate has been accounted for. For comparison, it is expected that the frequentist repeated measures model used for simulation is quite similar in relation to performance to the primary Bayesian repeated measures model.

22 Statistical Software

The statistical software used will be SAS[®], version 9.4 or later, and R, version 3.12 or later, respectively. For R, the packages Jags and Coda would be required to run the MCMC procedures.

23 Changes to Analyses Specified in the Protocol

• According to SAP section 16.1.4, TEAEs will be assigned to two periods rather than four periods as described in Protocol section 16.10.1, the reason being that the safety follow up periods following the DBP and the OLEP, respectively, will be part of the reporting periods rather than individual periods. In this way the first safety follow up period following the DBP will be reported as part of the DBP, and the safety follow up period following the OLEP will be reported as part of the OLEP.

24 Details on Data Handling

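### SAP 16.7 plans only a listing of MRI safety findings, where the protocol promises a summary by period and treatment group, and SAP section 23 does not declare the change

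*SAP*

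**What the plan says.** Both documents make MRI findings a safety endpoint of the double-blind period. The protocol synopsis has "Findings on MRI during the DBP, as specified in the" Imaging Charter, and SAP 4.4.1 has "Findings on MRI, as specified in the" Imaging Charter.

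The protocol commits to a summary in two places. Section 17.10.2 says "ADA, safety MRI findings and C-SSCS will be summarized by period and treatment group". The statistical methodology part of the synopsis says "MRI findings, and presence of ADAs will be summarized using descriptive statistics".

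SAP 16.7 says "MRI safety findings will be listed" and nothing more. SAP section 23, which records departures from the protocol's analyses, contains one item: "TEAEs will be assigned to two periods rather than four periods". MRI is not mentioned there.

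Under Panel 2 of the protocol, safety scans are due at baseline and at Weeks 12, 24 and 48. A further scan is due at end of treatment or withdrawal, but only if none was done in the preceding 8 weeks (footnote n). The synopsis gives oedema, microhaemorrhages, infarcts and meningoencephalitis as examples of what the scans look for.

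**The concern.** The protocol's promise and the SAP's plan are different outputs, and the difference is not declared. A summary by treatment group gives the number of patients with a finding, the number assessed and a percentage in each arm. A listing gives individual records. If the SAP is followed as written, the study report can meet the SAP and still contain no incidence by arm for an endpoint that both documents name.

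What is at stake is the description of MRI findings that are new on treatment but that the investigator does not judge clinically significant. These would be visible only patient by patient, with no stated denominator and no side-by-side comparison with placebo.

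**Working it through.** The plan states no figure on this point, so there is nothing to reproduce. The check is whether any other part of the SAP supplies the summary that 16.7 leaves out.

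**1. SAP 16.2, general methodology for other safety data.** It says that tables and graphs are by treatment group, but that governs how a table looks and does not create one. Its rule for descriptive statistics covers absolute values and changes from baseline, which suits numeric measurements. Its rule for counts and percentages covers potentially clinically significant (PCS) values. Appendix V sets PCS criteria for laboratory tests, vital signs, weight and ECG, and none for MRI. Neither rule therefore yields an MRI table.

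**2. SAP chapter 6, descriptive statistics.** It prescribes counts and percentages for categorical variables that are summarised. It does not say which variables are summarised.

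**3. Neighbouring sections.** SAP 16.5 (ECG) builds on the tables of 16.2 and adds categorical summaries. SAP 16.6 (C-SSRS) specifies numbers and percentages by treatment group. SAP 16.9 (deaths) specifies a summary by treatment group and, separately, a listing. So where the SAP intends both outputs it names both. Section 16.7 names only the listing.

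**4. Adverse-event tables.** Protocol 10.6.1 and 10.6.9 require clinically significant MRI changes to be recorded as adverse events. Protocol 11.1.1 defines clinically significant as suggesting disease or organ toxicity and needing active management, which includes further investigation or closer follow-up. SAP 16.1.3 counts an event as treatment-emergent if it starts or worsens on or after first dosing. SAP 16.1.6 tabulates these events, and protocol 17.10.1 presents them by period and treatment group. Clinically significant new MRI changes are therefore covered. Other new findings are not.

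**5. What the listing allows.** By SAP chapter 6, listings carry treatment group unless otherwise specified, so affected patients could be counted by hand. SAP 16.7 does not provide the number scanned in each arm.

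**6. Why the denominator matters.** Planned allocation is 40 to Lu AF82422 and 20 to placebo. As an illustration of the arithmetic only, suppose two patients in each arm have a new finding and all planned patients are scanned:

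- Lu AF82422: 2/40 = 5.0%
- Placebo: 2/20 = 10.0%

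Equal counts are a twofold difference in proportion. In practice the number scanned will not equal the number randomised. The sample-size section allows for 20% drop-out overall (0.20 × 60 = 12 patients), individual treatment lasts from 48 to 72 weeks, and the end-of-treatment scan is conditional.

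**Result.** Planned by-arm summaries of the MRI safety endpoint: none in the SAP, against a summary by period and treatment group in the protocol. Changes declared in SAP section 23 that concern MRI: none.

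**The case against.** The strongest reply is that the adverse-event route already covers what matters. The definition of clinically significant in protocol 11.1.1 is broad, such changes must be reported, and treatment-emergent events exclude unchanged baseline findings. This stands in large part. A reader might infer that the trial would have no by-arm rate for any MRI abnormality; the documents do not support that. The gap is confined to findings below the adverse-event threshold.

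A second reply is that 16.7 does not say that a listing is the sole output, and that SAP 16.3 and 16.4 also name no tables and rely on 16.2. That is fair for laboratory and vital-sign data, which fit the rules of 16.2. It does not carry over to MRI findings, which have neither change-from-baseline values nor PCS criteria. At best, 16.7 is ambiguous on a point where the protocol is definite.

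Two further inferences should be resisted. One is that MRI abnormalities are a known effect of this drug class. Protocol 5.1 gives as one reason for the independent monitoring committee "Use of a mAb, a new therapeutic, where other entities of the class had effects on the CNS", which concerns CNS effects in general and does not mention imaging. The other is that the listing would mix new findings with those present at baseline. The SAP does not describe the listing's content, so this is unknown.

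Finally, the monitoring committee reviews unblinded safety data about every 3 months during the double-blind period. That protects patients during the trial. It does not replace reporting the endpoint at the end.

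**Conclusion.** The point holds in a limited form. The SAP replaces a promised by-arm summary of a named double-blind safety endpoint with a listing and does not record the change. The consequence is that new MRI findings not judged clinically significant would have no planned incidence or denominator by arm. Efficacy conclusions, type I error and power are untouched, and clinically significant MRI changes remain visible in the adverse-event tables. The SAP should be amended.

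No numerical effect on the trial's conclusions can be given, because the documents state no expected rate of MRI findings. The 5.0% and 10.0% above only show why counts need denominators under 2:1 allocation. The conclusion assumes that SAP 16.7 will be carried out as written and that no summary is specified elsewhere. The Imaging Charter is not among the documents, so its categories of finding could not be checked.

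**What to change.** Add to SAP 16.7 one descriptive table for the double-blind period, by treatment group, based on the all-patients-treated set. For each Imaging Charter category, give n/N (%) of patients with at least one new or worsened finding after baseline. Let N be the patients with a baseline and at least one post-baseline safety MRI. State how new and worsened are judged against the baseline scan. Exact confidence intervals are optional, since the protocol commits only to descriptive statistics. Keep the listing.

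If the sponsor prefers a listing alone, SAP section 23 should say so and give the reason, because that departs from protocol 17.10.2.

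The cost is one table and a few lines of SAP text. It needs no new data, scans or readings beyond those the protocol already plans.
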